7.3 LOST TO FOLLOW-UP

The following actions must be taken if a parent/guardian of a participant fails to return or complete study assessments (on behalf of their enrolled child):

- Study staff will attempt to contact the parent/guardian of the participant and obtain the study survey data within 2 business days for weekly surveys and within 7 business days for quality of life surveys. They will also counsel the parent/guardian of the participant on the importance of maintaining the assigned study activity schedule on behalf of their enrolled child and ascertain if the parent/guardian of the participant wishes to have their child continue in the study.
- Before a participant is deemed lost to follow-up, the investigator or designee will make every effort to regain contact with the parent/guardian of the participant. See MOP for details. These contact attempts will be documented in the participant's study file.
- Should the participant's parent/guardian continue to be unreachable, he or she will be considered to have withdrawn from the study with a primary reason of lost to follow-up.

8 STUDY ASSESSMENTS AND PROCEDURES

8.1 EFFICACY ASSESSMENTS

Collection of participant characteristics and risk factors for recurrent wheeze:

History will be obtained at the start and end of the study to ensure randomization provides similar characteristics of the intervention and control groups. If there is an imbalance between arms, we will control for these factors in the primary analysis.

Table 4. Participant characteristics and risk factors for recurrent wheeze

Collect information at baseline or intervention start (by parental report unless otherwise indicated)

• Age (in months) at initial hospitalization for bronchiolitis (medical record review)• Gestational age at birth (parental report or medical record review)• Sex/gender (parental report or medical record review)• Race/ethnicity (parental report or medical record review)• Parental education• Rural/Urban (RUCA code) based on residential address• Viral test results (first hospital admission for bronchiolitis) if available per standard of care testing (medical record review)• Season of hospitalization for bronchiolitis (medical record review)• Highest level of respiratory support during bronchiolitis admission (medical record review)• History of previous wheezing with illness• Family history of asthma• Wood stove use in the home (and whether this is the primary heat source)

- Central air conditioning in the home
- Type of cooking stove in the home
- Presence of hood above cooking stove in home
- Use of hood while cooking
- Risk of higher frequency of viral exposures
 - Daycare attendance
 - Number of children in home
 - Number of children in home in daycare or school
 - Household crowding
- Presence of plumbed (running) water
- Furry pets in the home
- Baseline weekly average PM_{2.5} home measurements (Purple Air Monitor data report)
- Atopic dermatitis
- Chronic use of asthma medications preceding bronchiolitis hospitalization
- Use of asthma medications with illness preceding bronchiolitis hospitalization -
- Received systemic steroid during hospitalization for bronchiolitis (medical record review)
- Square footage of rooms containing HEPA units (during intervention set-up)
- RSV vaccination/preventive treatment history (by report from family or medical record review)

Collect information at approximately 26 weeks (end of 24-week intervention period) by parental report unless otherwise indicated

- Smokers who live in the home
- Chronic use of asthma medications -
- New prescriptions for asthma medications or antibiotics with healthcare visits for respiratory symptoms (determined from weekly survey entries)
- Atopic dermatitis
- Immunization status
- Average number of nights per week away from home (calculated from study data)
- Average number of days per week where the child was away from home more than 6 hours (calculated from study data)
- Model-estimated weekly outdoor PM_{2.5} concentration based on residential location (i.e., NOT parental reported) (These data may be obtained after the 26-week study period and/or after completion of the study.)
- RSV vaccination/preventive treatment history (by report from family or medical record review)

Air Quality Measurements (both intervention and control groups):

Family-collected with study team support remotely:

- Continuous PM Assessment: Families will install PurpleAir PA-II-SD (Appendix B) continuous sensors (<https://www2.purpleair.com/collections/air-quality-sensors/products/purpleair-pa-ii-sd>) in the common room and child's sleep space. The sensor measures numerous environmental factors, but PM_{2.5} concentration is of primary interest. The PurpleAir is 3.5 × 3.5 × 5 inches and weighs 25 ounces with the power supply. The distance from the filtration unit to the PurpleAir will be measured by the family with a tape measure and reported to the study team. Study team personnel will schedule a phone call or video meeting for each family to assist with equipment setup.
- Mean weekly indoor PM_{2.5} concentration is a secondary endpoint in the trial. Baseline (pre-intervention) PM_{2.5} will be measured ideally over at least four days.

Data from the PurpleAir can be stored and retrieved in two ways, both of which will be used in this study.

Title: *The BREATHE Study: Bronchiolitis Recovery and the Use of High Efficiency Particulate Air (HEPA) Filters*

Sponsor: ISCPTN DCOC

- Each PurpleAir is WiFi-enabled. When connected to WiFi, PurpleAir sensors transmit data to a PurpleAir server in real time. So that the monitor use does not interfere with a family's WiFi usage, each participating home will be provided with one mobile password-protected hot spot and necessary data. One hot spot is sufficient to serve both PurpleAirs. The PurpleAir monitors will be connected to the hot spot prior to mailing (done centrally prior to receipt of the monitors by individual study sites) to simplify set up of monitors by participating families.
- PurpleAir sensor data will be kept private to protect participant privacy. Data will be retrieved by University of Montana central site personnel from private sensors using a PurpleAir application programming interface (API) key using automated methods. For BREATHE homes able to transmit PurpleAir data through WiFi, data evaluation will occur in the first four weeks of study participation (approximately) to ensure the sensor(s) are operating properly. University of Montana central site staff will perform quality checks on the data, and, if issues arise, they will communicate with local site personnel to troubleshoot the problem or opt to rely on data from the security digital card (see below). If needed, staff will provide additional training or a new PurpleAir if there is a sensor malfunction. Also during the first four weeks of study participation (approximately), automated alerts to the central site to unusually high PM_{2.5} values will occur for BREATHE homes able to transmit PurpleAir data through WiFi. Should a 24-hour average exceed a 100 µg/cubic meter threshold, the University of Montana central site team will investigate further. Should a cleaned and corrected weekly average exceed that specified threshold, the local site will notify the family and provide informational resources on indoor air quality. Similarly, if the study team notices threshold exceedance at the end of a child's participation based on returned PurpleAir monitors and/or data transmitted through WiFi, the study team will notify the participant's caregiver and provide informational resources on indoor air quality.
- Each PurpleAir is equipped with a security digital (SD) card that logs PM_{2.5} data in the event of WiFi interruptions. The SD card has sufficient storage to hold at least 6 months of PM_{2.5} data so that it does not need to be changed during participation. The family will be instructed to mail the PurpleAirs back to the ISCPTN site (or designated central site, i.e., the University of Montana) at the end of participation. Research staff will then remove the SD card and download the data. Data from either WiFi or the SD card can be used to obtain the most complete and high-quality exposure assessment possible. The University of Montana central site team will provide final summary PM_{2.5} metrics to the DCOC.

Weekly survey collection of child's daily symptoms, healthcare utilization data, time away from home, and study equipment use:

The parent(s)/guardian(s) will submit a brief weekly online survey (via the EDC platform) that they receive via text or email. The alternative is a scheduled phone call with a standard script with the study coordinator or other qualified personnel from the study site research team. Parent(s)/guardian(s) of participants will receive a text or email reminder to complete the survey if it is not completed within 1 day of original due date. If a survey remains incomplete, the research team will continue to provide reminders to the parent/guardian until it is completed or closed.

The weekly survey will capture 4 elements: 1) the child's symptoms for the week, 2) number of healthcare visits, 3) time away from home, 4) study equipment use.

Each family will receive a visual tool (paper form named "Symptom Recall Tool") with the written questions as a prompt/reminder of what will be asked. The family will receive a booklet with a page of the Symptom Recall Tool for each week of the study. The Symptom Recall Tool is an aid for reporting and will not be collected. We estimate that the weekly survey will take 1-5 minutes to complete electronically.

- **Symptom survey:** The survey captures three daytime symptoms (cough, wheeze, trouble breathing) and nighttime awakenings due to cough. The responses to the symptom survey in the EDC will be used to determine SFDs. The questions have been used previously to measure SFDs after bronchiolitis over a similar time frame of approximately 6 months in a study testing whether an intervention reduces post-bronchiolitis symptomatic days.⁵

The questions are based on the Bronchiolitis Caregiver Diary, a validated measurement tool for respiratory symptoms after acute bronchiolitis.³⁷ These questions have been used to follow post-bronchiolitis symptoms over a 20-week period, similar to this study.⁵

- The survey will ask whether the child had any cough, wheeze, or trouble breathing this week (Y/N).
 - If No, they will move on to the next section for healthcare visits.
 - If Yes, they will receive a prompt for each day to respond Y/N for the presence of the symptom and if there are symptoms present, the survey will ask if any medications were used for respiratory symptoms (family to list names of medications).
- **Healthcare visits:** The parent/guardian will record the number of hospitalizations, ED/UC visits, and other medical visits for respiratory symptoms. This will be a (Y/N) for whether they participant (child) had a healthcare visit in the past week. If Y, there will be a prompt to enter the number of visits for each visit type. If N, they will move on to the next section, "Time away from home."
- **Time Away from home:**
 - **Days away from home:** The parent/guardian will be prompted to enter how many days that week the child spent more than 6 hours outside the home (0-7 days).
 - **Nights away from home:** The parent/guardian will be prompted to enter how many nights that week the child spent away from their primary residence (away for vacation, staying with someone else, etc.) (0-7 days).
- **Equipment use:**
 - **HEPA/control unit use:** For each room with a HEPA/control unit, the parent/guardian will be asked to respond Yes/No to whether they used unit and asked to report the usual setting used (1, 2, 3, or 4). If applicable, the parent(s)/guardian(s) will also record the numerical reading visible on the kW meter attached to each HEPA/control unit. This will be a simple entry of the numbers displayed on the kW meter to respond to the survey prompt.
 - **PurpleAir monitor:** The parent/guardian will be asked whether the monitor is plugged in with the light on (Yes or No). They will also be asked whether the hot spot is on with bar light and 3 lighted dots on (Yes or No).

Quality of Life:

- The PedsQL™ Pediatric Quality of Life Inventory Infant Scales⁹⁸ questionnaire will be administered to a parent/guardian at the end of the intervention period. This is a validated outcome measure of QOL for infants 1-12 months (36 items) and 13-24 months (45 items). The constructs include 5 subdomains: physical functioning, physical symptoms, emotional functioning, and cognitive functioning.

The questionnaire will be administered online. The alternative will be for the research coordinator to obtain responses verbally.

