9.4 STATISTICAL ANALYSES

9.4.1 GENERAL APPROACH

- **Descriptive Statistics:** All numerical variables will be summarized using mean \pm standard deviation and median (minimum, maximum). All categorical variables will be summarized using frequency (in %).
- **Inference tests:** All proposed statistical tests are two-sided. A p-value <0.05 is considered statistically significant.
- **Covariates:** Covariates will be compared between groups (intervention vs. control) using two sample t-tests, or Wilcoxon rank sum tests if they are continuous variables, and Chi-square tests or Fisher's exact tests if they are categorical variables. Each of the continuous covariate variables will be assessed of its correlation to the primary endpoint, or each of the secondary endpoints using a Pearson's correlation coefficient or a Spearman's correlation coefficient. Similarly, each of the categorical covariate variables will be assessed of its association to the primary endpoint, or each of the secondary endpoints using an ANOVA model, or a Kruskal-Wallis test. A covariate showing a significant association to intervention, a significant correlation or association to the primary (or secondary) endpoint will be considered as the adjusting (controlling) covariate and will be added as adjusting independent variable in the statistical models proposed for primary and secondary analyses.
- **Model assumptions:** Primary and secondary endpoints will be inspected of normal distribution assumptions using the histogram plots. If the variable is noticeably right (or seldomly left) skewed, then a transformation variable will be used in the parametric models to ensure the assumption of normality is met. As an alternative approach, a generalized linear model will be proposed to the variable using a distribution assumption fitting the data properly.

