9.4.2 ANALYSIS OF THE PRIMARY EFFICACY ENDPOINT

- **Primary Objective:** To test the efficacy of a HEPA filtration unit home intervention, relative to the control arm, with respect to respiratory symptom burden (as measured by symptom-free days; SFD) over 24 weeks following activation of filtration.
- **Primary Endpoint:** Number of caregiver-reported SFDs over 24 weeks following activation of filtration (SFD defined as a 24-hour period without coughing, wheezing, or trouble breathing)
- **Statistical Hypothesis:** Mean of SFDs in the HEPA filtration home intervention group is larger than mean of SFDs in the control group. The hypothesis testing is the comparison of superiority.
- **Statistical Procedures:** The hypothesis will be tested using a mixed effect model after accounting for within cluster correlation. The model uses the primary endpoint as the dependent variable, and the intervention effect (intervention vs. control) as the independent variable or the fixed effect with site as a random effect.
- **Missing Data:** The primary endpoint will be imputed if there is any missing observation in the ITT. The statistician will assess the missing patterns to determine if the cause of missing is missing at random (MAR), missing completely at random (MCAR), or missing not at random (MNAR). Imputation methods such as multiple imputation (MI) methods and pattern-mixture methods will be used in imputation and analyses.

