#### **Figure 1. Consort flowchart template for subject disposition**

#### 6.4. Participant Demographics and Baseline Variables

The participant demographics and baseline variables are summarized in Table 2. The baseline variables were collected after randomization but prior to intervention initiation.

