**Table 2. Summary of Baseline Characteristics and Covariates**

Sites	Variable	All N participants	Intervention Group	Control Group
Infant demographics				
Site 1	Infant's Age at initial hospitalization for bronchiolitis (in months), mean (SD)			

Gestational age at birth (in weeks), mean (SD)
Infant's Sex, N (%)
Infant's Race, N (%)
Infant's Ethnicity, N (%)
Rurality (RUCA code), N (%)
Parent/caregiver/legal guardian education, N (%)

---

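### Protocol 8.1 allows the primary analysis to adjust for end-of-study items that the filter could change, and the SAP does not withdraw that rule

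*Protocol*

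**What the plan says.** **Protocol 8.1 and Table 4.** The section opens with the purpose of the history: "History will be obtained at the start and end of the study to ensure randomization provides similar characteristics" of the two groups. The next sentence is the rule: "If there is an imbalance between arms, we will control for these factors in the primary analysis". Table 4 follows. Its first part is collected at baseline or intervention start, its second at about week 26. The second part includes chronic asthma-medication use and "New prescriptions for asthma medications or antibiotics with healthcare visits for respiratory symptoms". It also includes items the filter cannot touch, such as modelled outdoor PM2.5, described as a "concentration based on residential location (i.e., NOT parental reported").

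**Protocol 9.4.1.** A covariate significantly associated with arm or with an endpoint "will be added as adjusting independent variable in the statistical models proposed for primary and secondary analyses". No timing limit is set.

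**Protocol 9.4.2.** The primary hypothesis is tested in a mixed model that has "the intervention effect (intervention vs. control) as the independent variable or the fixed effect with site as a random effect". No covariate is named.

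**SAP 6.4, 6.5 and Table 2.** Table 2 is titled "Summary of Baseline Characteristics and Covariates" and contains no week-26 item. On timing, SAP 6.4 says: "The baseline variables were collected after randomization but prior to intervention initiation". SAP 6.5 starts from baseline characteristics, but its selection rule speaks of any variable associated with arm and endpoints, or with an association reported in the literature. Selected variables enter the primary and secondary models.

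**SAP 6.6.1.** The hypothesis test is attached to an arm-and-site count model. A multivariable model follows, with its own estimates, intervals and p-value.

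**SAP 1 and 7.** The SAP is to be read with the protocol. Section 7 is reserved for departures from the protocol's statistical approach and lists none.

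**The concern.** An end-of-study item cannot show whether randomization balanced the groups if the intervention can move that item. If active filtration reduces cough and wheeze, fewer children in that arm should be on asthma medication or receive new prescriptions at week 26. That difference between arms would be part of the treatment effect. Protocol 8.1 would treat it as an imbalance and control for it in the primary analysis, which removes some of the benefit the trial is meant to measure.

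The secondary issue is which result decides. Protocol 8.1, protocol 9.4.1 and SAP 6.5 put selected covariates into the primary model. Protocol 9.4.2 and SAP 6.6.1 state the test without them. The two selection rules also differ, so two analysts could build different adjusted models from the same data.

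**Working it through.** **Plan's own figure.** Inputs from protocol 9.2 and SAP 3.4: difference 20 days, SD 43, two-sided 0.05, power 90%. Then n per arm = 2 × (1.960 + 1.282)² × 43² / 20² = 97.1, rounded up to 98. With 98 per arm, 20 / (43 × √(2/98)) = 3.256, and the power is Φ(3.256 − 1.960) = 0.902 (0.900 by the noncentral t). The stated 98 per arm and 90% reproduce, for an unadjusted comparison.

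**Set-up for the 8.1 rule.** The documents give no correlation between a week-26 item and symptom-free days (SFDs), so the within-arm correlation r is assumed. Simulated trials have 98 per arm, normal SFDs with SD 43, and a linear model. The item is adjusted for only when it differs between arms at p<0.05.

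**Case A: the item is a consequence of symptoms.** The item depends on arm only through SFDs, and the true effect is 20 days. If the item is always adjusted for, the expected estimate is 20 × (1 − r²):

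| r | Always adjusted: 20 × (1 − r²) | 8.1 rule fires | Mean effect under 8.1 rule | Power under 8.1 rule |
|---|---|---|---|---|
| 0.2 | 19.2 days | 10% | 19.7 days | 89% |
| 0.3 | 18.2 days | 16% | 19.3 days | 88% |
| 0.5 | 15.0 days | 37% | 17.0 days | 83% |

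Unadjusted, the values are 20 days and 90%. With no true effect, rejection under the rule is 0.050 / 0.049 / 0.042, so type I error stays near or below 5% in this case.

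**Case B: the filter moves the item directly and has no effect on SFDs.** The filter lowers the item by s SD. The expected adjusted estimate is −43 × r × s:

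| r | s | −43 × r × s | Two-sided rejection under 8.1 rule |
|---|---|---|---|
| 0.3 | 0.3 | −3.9 days | about 8% |
| 0.3 | 0.5 | −6.5 days | about 18% |
| 0.5 | 0.3 | −6.5 days | about 14–15% |
| 0.5 | 0.5 | −10.8 days | about 46–47% |

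The bias runs against the filter, so this is not a route to a false claim of benefit.

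**Case C: two p-values and no stated deciding model.** With no true effect, and an item that differs between arms only by chance, counting either the unadjusted or the adjusted p-value gives rejection of about 0.058 / 0.064 / 0.073 for r = 0.2 / 0.3 / 0.5, or roughly 6–7%.

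**The case against.** The best defence is that the SAP already points the right way. Its covariate table is confined to pre-intervention items. Its selection paragraph begins from baseline characteristics. Its adjusted model is for potential confounders, and a consequence of treatment is not one. The purpose stated in 8.1, checking randomization, makes sense only for factors that precede treatment. All of that stands, and it makes the harmful reading less likely. It does not remove it: 8.1 expressly covers end-of-study history, the selection rule in SAP 6.5 has no timing limit, and section 7 records no departure.

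On the deciding model, both documents attach the hypothesis test to arm and site, and the power calculation is unadjusted. A reader might infer that the plan leaves the choice of model wholly open. The documents do not support that. The arm-and-site model is the natural reading, and what remains is a conflict with the three places that add covariates to the primary models.

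The sizes are also open to challenge. The correlations and shifts are assumed, the simulated item is continuous whereas medication use is categorical, and the model is linear rather than the SAP's log-link count model on 0 to 168 days. The figures show direction and range only. It would also be wrong to measure the harm by the gap between adjusted and unadjusted estimates in just those trials where the rule fires. Those trials are selected partly for chance imbalance, and their unadjusted estimates average above the true 20 days.

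**Conclusion.** The concern holds as a defect of specification. The protocol's rule reaches week-26 items that a working filter could change, and nothing in the SAP cancels it. The wording is certain. The size rests on the assumptions above.

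For an item that is purely a consequence of symptoms, the average loss is small at correlations of 0.2 to 0.3 (about 0.3 to 0.7 days and 1 to 2 points of power). It becomes material at 0.5 (about 3 days and 7 points).

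No single statement about type I error is right. It stays near or below 5% only if the item depends on arm solely through SFDs. It can be well above 5%, with bias against the filter, if the filter moves the item directly. It is about 6–7% if either p-value may count.

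A reader might infer that the trial will in fact adjust for medication use at week 26. The documents do not show that; they fail to rule it out. The sample size is unaffected. The correction should be made, and it is inexpensive.

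**What to change.** 1. In protocol 8.1, replace the imbalance sentence with: *Only variables measured before filter start, or variables the intervention cannot affect (such as modelled outdoor PM2.5), may be adjusted for in an efficacy model.* Report the other week-26 items by arm only.
2. State the same limit in protocol 9.4.1 and SAP 6.5. Replace the two selection rules with one covariate list, fixed before any unblinded comparative data are seen, including those of the interim analysis. Record this in SAP section 7.
3. State in protocol 9.4.2 and SAP 6.6.1 that the arm-and-site model, already tied to the hypothesis test, decides at both the interim and the final analysis. Label the adjusted model supportive.

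The cost is a few sentences and no new data. Under the protocol's Statement of Compliance, protocol edits need approval from the reviewing IRB. A SAP clarification can come first, with the protocol aligned at its next amendment.
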